**Table 3 Censoring rules for PFS**

Situation	Date of Event or Censoring
No CT assessment at baseline	Date of first study treatment administration
No progression nor death nor non-trial systemic anti-cancer treatment documented	Date of last post-baseline CT assessment
Death more than [REDACTED] after last post-baseline CT assessment	Date of last post-baseline CT assessment
Death more than [REDACTED] after first study treatment and without post-baseline CT assessment	Date of first study treatment administration
Progression criteria met after $\geq 2$ consecutive schedule missing CT assessments	Date of last post-baseline CT assessment before missing CT assessment
Progression criteria met [REDACTED] after previous CT assessment	Date of previous CT assessment

OS is defined as the period from the first dose of study drug until death due to any cause.

Patients alive at their last visit will be censored at the last visit date.

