### 3.2.2 Secondary endpoints

The key secondary objectives of the trial are:

- Percentage of patients with shown immunogenicity

[figure not shown]
to EO2316, EO2317, EO2318, and UCP2 that compose EO2401

[figure not shown]
Cross reactivities with the human TAAs IL13Ra2, FOXM1, and BIRC5/survivin will also be evaluated

[figure not shown]
The other secondary endpoints of the trial are:

- ORR, time to response, and DOR as described by RECIST 1.1 [36] and iRECIST criteria [37]; see [Section 12.1](#) for an outline of response criteria.
- PFS as described by RECIST 1.1 and iRECIST criteria, defined as the time interval from the date of first study treatment administration to the date of progression (by RECIST 1.1 or iRECIST criteria) or death due to any cause, whichever is earlier. Patients without progression or death are to be censored at the time of the last tumor assessment.
- OS defined as the time interval from the date of first study treatment administration to the date of death due to any cause. Patients alive will be censored at the date of the last documented follow-up.
- In addition, in the randomized extension of Cohort 2A safety and tolerability of EO2401/nivolumab will be assessed versus internal concurrent controls (groups of patients treated with EO2401 monotherapy and nivolumab monotherapy, respectively), by incidences of adverse events (AEs), treatment-emergent AEs (TEAEs), serious AEs (SAEs); AEs will be analyzed irrespective of relationship, and as related events.

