## 7.5 Visits during post-treatment follow-up

### 7.5.1 Post-treatment visit for safety assessment; Vn+1

A post-treatment safety assessment visit should be performed 30 days after the last study treatment has been administered.

The following will be done during the visits:

- documentation of concomitant medications/treatments,
- measurement/assessment of:
  - weight, and ECOG performance status (see [Section 12.2](#)),
  - vital signs, and major body systems via physical examination, as outlined in [Section 7.3](#),
  - safety blood samples [REDACTED]
  - for women of childbearing potential, highly sensitive serum pregnancy test,
  - assessment of a 12-lead ECG,
- adverse events will be recorded according to NCI-CTCAE v5.0 (AEs will be monitored for the whole duration of the trial, but assumed recorded at visits for treatments, except in cases where the seriousness demands more immediate reporting, see [Section 8](#)), and

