### 7.5.3 Post-treatment follow-up; Vnnn

Patients will be followed [REDACTED]

At these [REDACTED] timepoints, which if the patient is unable to attend a site visit can be a telephone contact, the following will be done:

- survival status documentation (in case of death, an as precise as possible cause of death is going to be documented),
- documentation of safety; after the post-treatment visit for safety assessment (see [Section 7.5.1](#)) has been made, only SAEs with plausible causal relationship with trial treatment will be documented, and
- if applicable, collection of information regarding further anti-cancer treatments.

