All data generated from external sources (e.g. central laboratory) and transmitted to the Sponsor or designee electronically will be integrated with the patient's eCRF data in accordance with the Data Management Plan.

An eCRF must be completed for each patient who signs an ICF and undergoes any pre-screening or screening procedures, according to the eCRF completion instructions. Automatic validation programs check for data discrepancies in the eCRFs and, by generating appropriate error messages, allow modification or verification of the entered data by the Investigator staff before transfer of data to the Sponsor (or a designated CRO).

Sponsor personnel (or a designated CRO) will review the eCRFs entered by site staff for completeness and accuracy (verification against source documents) and instruct the site personnel to make any required corrections or additions. System or manually generated queries are raised to the investigational site using the study EDC system. Designated Investigator/site staff is required to respond to the queries and make any necessary changes to the data.

The Investigator will sign and date the eCRF via the EDC system's electronic signature procedure. These signatures will indicate that the Investigator reviewed and approved the data on the eCRF, the data queries, and the site notifications.

At the conclusion of the study, the occurrence of any protocol deviations will be determined (guidance can be found in Section [12.4](#)).

After these actions have been completed and the database has been declared to be complete and accurate, it will be locked.

After database lock, the Investigator will receive a CD-ROM of the patient data for archiving at the investigational site.

A specific EDC tool will be used after the database lock planned at the last safety visit of the last treated patient, to collect the survival data of all patients who will be followed until death or until sponsor decides to stop the study.

Following the final safety visit of the last treated patient and the subsequent database lock, the sponsor will internally utilize an EDC tool compliant with 21 CFR Part 11 to collect survival data. Survival data will be transmitted directly from the investigational sites to the sponsor, who will then integrate these data into the EDC system.

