#### 3.1 Analyses planned and already performed

The nature of the study, i.e. an early exploratory development trial aiming at generating as much knowledge as possible before potential decisions related to further development of EO2401, makes it important to assess especially safety, but also efficacy and possible biomarkers, on an ongoing basis during trial conduct. Exploratory preliminary data from the trial might be utilized in relation to e.g. scientific discussions and presentations to facilitate input regarding possible improvements of development parameters.

In particular, the independent data monitoring committee (IDMC) will examine the safety of study participants throughout the duration of the study. The IDMC will examine the safety data of Cohort 1, including possible transitions between sub-cohorts (1a, 1b, 1c, and 1d) and provide advice and guidance regarding the recruitment start of Cohorts 2A, 2B, 3A, and 3B. The safety of patients in Cohorts 2A, 2B, 3A and 3B are also subject to assessments of the IDMC. In addition, in relation to the randomized extension of Cohort 2A, the IDMC will oversee and validate the interim first stage analysis of the Simon's two-stage design as performed by the Sponsor (or designee); see Section 9.4.2 of the protocol.

This SAP covers the analyses of the study which will constitute the content of the primary Clinical Study Report (CSR) and the needed addenda.

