#### **7.8.6 Progression-free survival (PFS) and overall survival (OS)**

According to RECIST, PFS is defined as the period from the first dose of study drug until PD or death from any cause (whatever occurs first).

PFS is defined as the period from the first dose of study drug until the first time one of following events occurs

- Progression criteria according to iRECIST/RECIST met

- Start of non-trial systemic anti-cancer treatment (which is regarded as progression according to the protocol).
- death from any cause [REDACTED] after last post-baseline CT assessment [REDACTED] after first dose of study drug, if no post-baseline CT assessment is available.

Non-trial systemic anti-cancer treatment is defined as concomitant or post-study treatment/medication that is classified as chemotherapy in the eCRF. Mitotane therapy is not considered as non-trial system anti-cancer treatment.

According to RECIST the progression criteria is met at the first date of post-baseline CT assessment with PD documented as response, if not more than one scheduled CT assessment is missing or not evaluable before this CT assessment and the previous CT assessment was performed within [REDACTED] to this CT assessment.

According to iRECIST the progression criteria is met at the date of CT assessment with response documented as iUPD for that the next CT assessment documents iCPD as response (without any intervening assessments with other outcome), i.e. PD is confirmed, and if not more than one scheduled CT assessment is missing or not evaluable before the CT assessment with iUPD documented and the previous CT assessment was performed within [REDACTED] to CT assessment with IUPD documented. If progression is not confirmed and there is no subsequent CT assessment with iSD, iPR or iCR as response then the iUPD date will still be used as date of progression met in the following scenarios:

- no further response assessments are done or
- the next timepoint responses are all iUPD, and iCPD never occurs.

Non-trial systemic anti-cancer treatment is defined as concomitant or post-study treatment medication that is classified as chemotherapy in the eCRF. Mitotane therapy is not considered as non-trial system anti-cancer treatment.

Patients without an event as defined above will be censored based on the rules in Table 3.

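### The SAP censors OS at the last visit, not at the protocol's last documented follow-up; this can bias OS downward in updates after database lock

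*SAP*

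**What the plan says.** **Censoring date.** Protocol 3.2.2 defines OS from first dose to death from any cause and adds: "Patients alive will be censored at the date of the last documented follow-up". SAP 7.8.6 keeps the event definition but, just below Table 3, says: "Patients alive at their last visit will be censored at the last visit date". The SAP does not say what counts as a visit for this purpose.

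**Who is censored.** For PFS the same SAP section is explicit: "Patients without an event as defined above will be censored based on the rules in Table 3". The OS sentence carries no such condition.

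**Survival contacts before lock.** The Vnnn time points sit in Protocol 7.5, headed "Visits during post-treatment follow-up". Section 7.5.3 says of them: "which if the patient is unable to attend a site visit can be a telephone contact".

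**Survival data after lock.** Protocol 10.7 states: "A specific EDC tool will be used after the database lock planned at the last safety visit of the last treated patient", and also: "Survival data will be transmitted directly from the investigational sites to the sponsor". No visit is described.

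**Scope.** SAP 3.1 says that the SAP governs "the content of the primary Clinical Study Report (CSR) and the needed addenda", so the OS rule applies to updates as well. SAP 7.8.7 plans Kaplan-Meier plots, quartiles and survival estimates at 6, 12, 18 and 24 months.

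**The concern.** Every patient who attended a visit was alive at it. Read alone, the OS sentence therefore also covers a patient who was alive at the last visit and died later, who then meets both the event rule and the censoring rule. Such deaths are foreseen: Protocol 5.3.6 records a retrievable date of death even after complete withdrawal of consent.

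The practical question is what happens to survivors in an update. A death reported after lock has a date and will naturally be counted. A report that a patient is alive may carry no visit date, and the SAP rule then leaves that patient censored at the last pre-lock visit. Survivors leave the risk set early while deaths from the same period stay in, so censoring depends on outcome and the curve falls too low. At stake is a descriptive secondary endpoint, mainly for the cohort recruited last, such as randomized Cohort 2A-I (13 patients).

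**Working it through.** Neither document attaches a sample size, power or event count to OS, so there is no plan figure to reproduce. The check compares the two rules and then sizes the difference.

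**Mechanism.** Take two patients first dosed 20 months before lock, with contacts every 3 months and an update 6 months after lock, at month 26. The last pre-lock contact is at month 18 and the last contact before the update at month 24. One patient dies at month 23; the other is alive. Under the protocol rule the survivor is censored at month 24, so the death is 1 of 2 at risk. If the survivor stays at the last pre-lock visit (month 18), the death is 1 of 1 at risk.

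**Inputs from the protocol.** Median OS for ACC, for illustration: 10.6 months (avelumab trial, 1.2), 14.8 months (first-line chemotherapy trial, 1.1.1) and 24.9 months (pembrolizumab trial, 1.2).

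**Assumed inputs.** Exponential OS; uniform entry over E = 24 months; contacts every 3 months (the interval is redacted); lock L months after last entry; update U = 6 months after lock.

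**Formulas.** For a patient entering at month a, time from first dose to lock is L + E − a, and to the update L + E − a + U. Deaths up to the update count under both rules. Survivors are censored at the last 3-monthly contact before lock (SAP wording, post-lock alive reports carrying no visit date) or before the update (protocol wording). True 24-month OS is 0.5^(24/median): 20.8%, 32.5% and 51.3%.

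**Primary report (U = 0, Vnnn contacts counted as visits).** Both rules give the same dates. At L = 12, 24-month OS is 19.4%, 30.9% and 49.7% under either rule: gap 0.

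**Update with U = 6, L = 12.**

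| Median OS (months) | SAP wording | Protocol wording | Gap (points) |
|---|---|---|---|
| 10.6 | 16.7% | 20.2% | 3.5 |
| 14.8 | 27.3% | 31.8% | 4.5 |
| 24.9 | 45.8% | 50.6% | 4.8 |

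The gap is about 2 points at 18 months and 0 at 12 months.

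**Effect of lock timing on the 24-month gap (E = 24, U = 6).**

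| Lock after last entry (months) | Gap (points) |
|---|---|
| 12 | about 3.5 to 5 |
| 15 | about 2 to 3 |
| 18 | about 1 to 2 |
| 25 | 0 |

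**Effect of entry length.** With 12-month entry and updates at 6 to 12 months, the gap is 4.4 to 10.2 points for lock at 15 months, 1.7 to 4.4 at 18 and 0 at 25.

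**Common cut-off.** The protocol wording itself falls slightly short of the true values (20.2% against 20.8%, for example), because deaths are counted up to the update but survivors only to their last contact. Applying one cut-off to both, with alive status known at the cut-off, returns 20.8%, 32.5% and 51.3%.

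**The case against.** **The event condition.** Death is named as the OS event in the sentence immediately before. PFS needs an explicit condition because it has several event types and Table 3 turns some deaths into censorings; OS has one. This largely stands. A reader might infer that the SAP censors every patient and leaves no OS events, but the definition makes that reading implausible.

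**The primary report.** A reader might infer that OS there is already biased. The protocol does not support that: survival contacts are classed under visits and may be by telephone, so the last visit and the last documented follow-up can be the same date.

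**Updates.** Protocol 10.7 changes the capture tool; it does not say that contacts stop or that only deaths are recorded. This stands too: neither document says that post-lock reports of living patients will be ignored. But the SAP anchors censoring to a visit date, and the post-lock route has no visit, so the wording does not prevent it. Nor can the change of rule be called undeclared, because SAP 5.3 is redacted.

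**Lock timing.** From protocol version 5.0 (24 January 2024, when all 70 patients had been treated) to the SAP (6 November 2024) is 287 days, or 287/30.5 = 9.4 months. A reader might take that as the earliest lock and quote larger gaps. It concerns the lock for the primary report (SAP 5.2), whereas the survival tool starts after the lock at the last treated patient's last safety visit. Cohort 2A-I probably had longer follow-up in any case. Recruitment was to pause once 13 patients had started the combination (SAP 4.3), the cohort has 13, and Protocol 10.3 treats the stage 1 result as known. If stage 1 was read at day 169 (169/30.5 = 5.5 months), last entry was at least 9.4 + 5.5 = about 15 months before the SAP date. Non-randomized Cohort 2 was analyzed before the extension opened, so its gap is smaller.

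**Precision.** At median 14.8 months, with lock at 12 months, the gap of about 4.4 to 4.5 points compares with a sampling SD of about 13.5 points for 13 patients and 9.5 for 26. The gap is well inside the noise, but it is systematic and avoidable.

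**Conclusion.** The conflict is real and minor. The SAP replaces the protocol's censoring date with a narrower, undefined one and omits the event condition that it uses for PFS. Confidence is high for the wording conflict, and for the downward direction if post-lock deaths count while survivors stay at their last pre-lock visit. It is not high for whether that handling would occur, nor for its size, which depends on entry and lock timing that the documents do not give.

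A gap of zero at 24 months is possible: if the last patient to enter were treated for the maximum 24 months and had the 30-day safety visit, lock would come about 25 months after last entry (24 + 30/30.5). The phase 2 primary endpoint, the 6-month PFS rate, is unaffected.

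**What to change.** Replace the OS censoring sentence in SAP 7.8.6 with:

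*All documented deaths up to the survival cut-off are events; patients not known to have died by then are censored at the last date known alive from any source (visit, telephone contact or post-lock survival update), not later than the cut-off, with the same cut-off applied to deaths and alive status.*

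Add a last-known-alive date to the post-lock survival tool. SAP 7.6 already uses such a date when imputing partial death dates, so the concept is not new to the plan. The cost is one sentence and one data field, with no extra visits or patients. It should be settled before the first OS addendum.

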### 7.8.7 Analyses of DOR, time-to-OR, PFS and OS endpoints

DOR, DDC, time-to-OR, PFS and OS will be described by KM plots along the number of patients at risk. Separate plots will be created including the curves of following cohorts:

- Cohorts 2A, 2B, 3A, and 3B, non-randomized
- Cohorts 2A, 2B, and 2, non-randomized
- Cohorts 3A, 3B, and 3, non-randomized
- Cohort 2A-I, Cohort 2A-II, and Cohort 2A-III, randomized
- For patients fulfilling and not fulfilling extended in/exclusion criteria of Cohorts 2A, non-randomized

The number of patients with an event of interest and being censored and the median, as well as 1st and 3rd quartiles of the estimated times of interest will be presented with their associated two-sided 95% CIs according to Klein and Moeschberger using a log-log-transformation. If reasonable, non-parametric competing risks techniques will be applied for time-to-OR as a sensitivity analysis, if a non-negligible number of deaths is recorded without earlier objective responses. For PFS and OS, 6-months, 12-months, 18-months, and 24-months PFS/survival estimates and corresponding 95% pointwise confidence limits will be provided in addition.

If the number of events is sufficient, DOR, time-to-OR, PFS and OS will be analyzed using Cox proportional hazards model. For Cohort 2 and 3, non-randomized, the following covariates will be included in the Cox-proportional hazards model

- Primary diagnosis (ACC vs. MPP)
- Previously treated (yes vs. no).

For cohort 2, randomized, the variable cohort (Cohort 2A-I, Cohort 2A-II, vs Cohort 2A-III) will be included in the Cox-proportional hazards model as covariate. No Cox-proportional hazard models will be provided for by patients fulfilling and not fulfilling extended in/exclusion criteria of Cohorts 2A, non-randomized.

All results of the CT scans will be listed.

### 7.9 Immunogenicity

As described in Section 5.1, the FAS Population will be the basis for the analysis of immunogenicity data. Only summary tables for Cohorts 2 and 3, non-randomized, with columns for Cohorts 2A, 2B, 3A, 3B, and totals for 2A and 2B together, and for 3A and 3B together and a total column for Cohorts 2 and 3 combined, and Cohort 2, randomized with columns for Cohorts 2A-I, 2A-II, 2A-III, and a column presenting all cohorts that were treated with EO2401 as monotherapy or in combination with Nivolumab (i.e. all cohorts, randomized and non-randomized), and none for Cohort 1 are planned.

#### 7.9.1 Definition of tests, parameters and possible results

[REDACTED]

Positivity and boosting criteria are defined as follows:

A 10x10 grid of black bars representing data points. The bars are arranged in a pattern where most are long and thin, with a few larger, shorter bars and a few very small bars. The grid is composed of 100 bars in total.

The figure consists of a 4x4 grid of 16 black bars. The bars are arranged in four rows and four columns. The bars in the first and third columns are very long, while the bars in the second and fourth columns are very short. The bars in the second and fourth rows are also very long, while the bars in the first and third rows are very short. The bars are black on a white background.

## 7.9.2 Analysis of immunogenicity test results

For T cell immunogenicity, the following analyses of immune response will be provided [REDACTED] at Screening and at different timepoints detailed in the Schedule of Assessments:

- The immunogenicity of the 4 compounds (EO2316, EO2317, EO2318, and UCP2) separately or as a pool (according to availability from central laboratory)
  - Frequency of positive patients.
  - Frequency of patients with boosting response (only for post-Screening assessments).
  - For the two above analyses, two types of denominators will be used: the first will be the number of patients with available test results at the given visit, the second will be the number of patients in the cohorts.

the immunogenicity of each of the 4 compounds (EO2316, EO2317, EO2318, and CP2) separately or as a pool (

by visit:

- Frequency of positive patients.

For analysis, the baseline value will be defined as last scheduled or unscheduled value collected prior to the first dose of treatment.

A listing of T cell immunogenicity results will be provided, with presence of positive/boosting response from each test and each compound, by patient and by visit.

- Cross reactivities of the 3 compounds (EO2316, EO2317, EO2318) with the three human TAAs (IL-13Ra2 and BIRC5 (survivin) and FOXM1):
  - Prior to cross-reactivity, positivity of human TAAs as pool will be analyzed

As before, we will use two types of denominators: the first will be the number of patients with at least one available test result among the 3 tests at the given visit, the second will be the number of patients in the cohorts.

For more information, contact the Office of the Vice President for Research and Economic Development at [contact] or [[contact]](mailto:[contact]).

## 7.10 Exploratory endpoints

A horizontal bar chart consisting of 20 black bars of varying lengths. The bars are arranged in two main groups: a top group of 10 bars and a bottom group of 10 bars. The bars in the top group are generally longer than those in the bottom group. The bars are set against a white background with a light gray horizontal grid.

Term	Percentage
GMOs	~75%
Organic	~95%
Natural	~95%
Artificial	~65%
Organic	~95%
Natural	~95%
Artificial	~65%
Organic	~95%
Natural	~95%
Artificial	~65%
Organic	~95%
Natural	~95%
Artificial	~65%
Organic	~95%
Natural	~95%
Artificial	~65%

